Blood samples taken via an intravenous access will be sent to biochemistry laboratories for further examinations. When collecting blood, some patients may experience minor discomfort when the needle penetrates the skin and rarely a small bleeding occurs. The amount of blood collected during the entire study period is a maximum of 196 ml (28 ml per visit), which equals less than half of what is in a normal blood donor sample.

Joint aspirations

If patients experience a gout attack with accumulation of fluids, ultrasound guided aspirations from affected joints will be conducted (the joint will be emptied so the amount varies and cannot be specified beforehand). Aspiration of the synovial fluid requires insertion of a needle in the patient's joint. Patients may experience some discomfort when the needle penetrates skin and synovium. The procedure will be done according to current standards for hygiene and aseptic injection technique. Penetrating the skin always carries the risk of infection, but the joint aspirations are standard care and the incidence of procedure related infections is very small. The procedure is considered to be justifiable from a health research ethical perspective.

Protocol amendments

None declared. However, any modifications to the protocol which may impact on the conduct of the study, potential benefit of the participants or may affect participant safety, including changes of study objectives, study design, study population, sample sizes, study procedures, or significant administrative aspects will require a formal amendment to the protocol.

Consent or assent

Additional consent provisions for collection and use of participant data and biological specimens in potential ancillary studies: Ancillary studies involve the collection or derivation of data for purposes that are separate from the main trial. The acquisition and storage of data and biological specimens for ancillary studies is increasingly common in the context of clinical trials. Specimens may be used for a specified subset of studies or for submission to biorepositories for future specified or unspecified research.

Confidentiality

Participant confidentiality

This study will be conducted under related legislation and regulations, including the Danish Act on Processing of Personal Data.

Participant medical information obtained by this study is confidential, and disclosure to third parties is prohibited.

With the participant's permission, medical information may be shared with his or her personal physician or with other medical personnel responsible for the participant's welfare.

If the data from this study are published, the presentation format will not include names, recognizable photos, personal information or other data which compromises the anonymity of participating participants.

All study-related information will be stored securely at the study site (The Parker Institute, Bispebjerg and Frederiksberg Hospital). All participant information will be stored in locked file cabinets in areas with limited access. All laboratory specimens, reports, data collection, process, and administrative forms will be identified by a coded ID number only to maintain participant confidentiality. All records that contain names or other personal identifiers, such as locator forms and informed consent forms, will be stored separately from study records identified by code number. All local databases will be secured with password-protected access systems. Forms, lists, logbooks, appointment books, and any other listings that link participant ID numbers to other identifying information will be stored in a separate, locked file in an area with limited access.

Notification to the Danish Data Protection Agency

Because the study is carried out at hospital departments, it is regarded as "public" in accordance with the Data Protection Agency guidance. The study will be notified to the Data Protection Agency.

Insurance

The participants are insured by the Danish Patient Insurance Association. Financing and insurance issues are addressed in the written information material.

Declaration of interests

Financial and other competing interests for principal investigators for the overall trial and each of the trial investigators: This study had no financial competing interests. The Parker Institute is grateful for the financial support received from public and private foundations, companies and private individuals over the years. The Oak Foundation is a group of philanthropic organisations

that, since its establishment in 1983, has given grants to not-for-profit organisations around the world. Drs. [name], [name], [name], and [name] report having previously received travel and/or research grants from the Cambridge Manufacturing Company to attend scientific meetings; holds no shares or share options in the company. Neither the investigators nor any of the other members of the project group has financial interest in the conduct or the results of the trial.

Access to data

All investigators will be given access to the cleaned data sets. Project data sets will be housed at the Parker Institute, Bispebjerg and Frederiksberg Hospital; all data sets will be password protected. To ensure confidentiality, data dispersed to project team members will be blinded of any identifying participant information.

Ancillary and post-trial care

Provisions, if any, for ancillary and post-trial care and for compensation to those who suffer harm from trial participation: Should this study provide apparent evidence for the effectiveness of weight reduction to patients with gout, it will be critical to provide access to the effective product(s) to study participants who were randomly allocated to the Conventional Diet (Control) group. In preparation for this study (protocol), discussions have begun with Cambridge Manufacturing Company to ensure such access (30 patients allowed 16 weeks of free products including support from the dietitians).

Dissemination policy

The results are to be reported according to the CONSORT guidelines {Moher, 2010 #22}: Negative, positive and inconclusive results will be disseminated in international peer-reviewed scientific journals at national and international conferences. Access to data can be granted on approval for a formal request to the trial steering committee. The scientific integrity of the project requires that the data from the 'Weight Loss for Gout' trial will be analysed study-wide and reported as such. All presentations and publications are expected to protect the integrity of the major objective(s) of the study; interim analyses will not be performed. Recommendations as to

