In general, the cognitive behavioural therapy provided with the dietary approach focuses on long-term lifestyle modifications; educational themes are: energy expenditure and energy balance, macronutrients, satiety, digestion, motivation and diet planning. The group treatment provides a combination of empathy, social support. In both phases of the study, the dietitian will aim to maximise adherence by reinforcing positive dietary changes and addressing barriers to adherence.

Conventional Diet (CD) Group: The programme will consist of a presentation by the same dietitian as for the ID group, who will provide nutritional advice in a 2 h session at baseline (week 0), and in week 8. At these sessions the dietitian will recommend eating ordinary foods in amounts which will provide the patients with approximately 5 MJ/day (1,200 kcal per day). The follow-up meeting at week 16 will not influence the outcome. Thus, during the 16 week trial, the CD group will attend three sessions altogether with a total of approximately 4h of instruction.

At the end of the study (16 weeks) all participants, both ID group and CD group, will be offered voluntary follow-up consultations with a dietitian at the Parker Institutes outpatient clinic.

Outcomes

Table 2 illustrates the time points at which the outcomes are assessed during the 'Weight Loss for Gout' study.

Table 2. Protocol schedule of forms and procedures

VARIABLE	Screening (approx. -2 wks)	Enrolment	Baseline (0 wks)	Intermediate (8 wks)	Endpoint (16 wks)
Secretariat:					
Information					
Motivational appraisal	X				
Eligibility criteria/Screening (phone)					
Informed consent		X			
Demographics and clinical features:					
Age, years		X			
Male, y/n		X			
Ethnicity, n (%)		X			
Duration of gout, years		X			
Height, cm		X			
Body mass index, kg/m ²		X	X	(X)	(X)
Flares* in the preceding year, count		X			
Presence of palpable tophi, y/n		X		X	X
Comorbidities:					
History of kidney stones, y/n		X			
History of gall stones, y/n		X			
Cardio Vascular Disease, y/n		X			
Diabetes, y/n		X			
Hypertension, y/n		X			
Hyperlipidaemia, y/n		X			
Urate Lowering therapy:					
Allopurinol, y/n		X			X
Febuxostat y/n		X			X
Probenecid y/n		X			X
Benzbromarone, y/n		X			X

Anti-inflammatory prophylaxis:				
NSAIDs, y/n		X		X
Prednisone, y/n		X		X
Colchicine y/n		X		X
Concurrent medication:				
Diuretics y/n		X		X
Aspirin y/n		X		X
Antihypertensive medication y/n		X		X
Lipid lowering agents y/n		X		X
Diabetes medication y/n		X		X

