A computer-generated randomisation sequence will be produced, before any participants are enrolled, that allocate participants in permuted blocks of 2 to 4 to the ID or the CD group (1:1). The randomisation sequence will be prepared using SAS Proc Plan; after the list has been generated it will be concealed in a password-protected computer file only accessible by the data manager ([name]). Randomisation will be stratified according to gender (M vs F), baseline obesity class (<40 vs. ≥ 40 kg/m²), and SU level (< 6 vs. ≥ 6 mg/dL). These eight mutually independent randomisation sequences (each including 60 “virtual patients”) will be entered into the eCRF by the data manager ([name]).

Allocation concealment and implementation:

Individual allocations will be held in pre-specified virtually sealed (opaque), consecutively numbered envelopes (see sequence generation). From the computer-generated sequence generation the formalised group allocation is revealed when the physician clicks on the ‘randomisation button’, appearing at the baseline visit in the eCRF system. Upon allocation to one of the two groups the patient identifier is automatically coupled to specific dietary plan/schedule. Thus the entire randomisation and allocation process will be concealed for all investigators, clinical, academic, and administrative trial personnel.

Virtual envelopes will be opened sequentially by an un-blinded study nurse. This procedure will ensure that participants, study staff, and outcomes assessors are blinded to group allocations at least until the individual participant attends the nutrition department at the Parker Institute.

Blinding (masking)

The term “blinding” or “masking” refers to withholding information about the assigned interventions from people involved in the trial who may potentially be influenced by this knowledge.

Blinding is an important safeguard against bias, particularly when assessing subjective outcomes. Participants included in the trial may respond differently (e.g. on patient-reported outcome measures) if they are aware of their treatment assignment (such as responding more favourably when they receive the new treatment). Lack of blinding may also influence compliance with the intervention, use of co-interventions, and risk of dropping out of the trial.

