However, in view of the use of a formula (liquid) low energy diet in the intensive weight loss group, as well as more attention provided from the dietitians, blinding of staff or participants will not be feasible. As a consequence, the possible influence of performance bias on patient-reported outcomes will be discussed as a possible limitation.

Statistical methods

Data will be analysed according to a pre-established statistical analysis plan (SAP). Primary analyses will be done on a modified ITT population, which include all randomised individuals who had the respective variable assessed at baseline. All analyses will be analysed and reported as two-sided, done at a 5% significance level.

We will use analysis of covariance (ANCOVA) for the continuous outcome measures modelled using repeated-measures (mixed linear model) analysis. The statistical model will include diet group (ID/CD) as fixed effects, an interaction between time and diet group, and the respective variable (e.g. body weight at baseline) as assessed at randomisation as covariate. Furthermore, the possible impact on the effect size of the factors used for the stratified randomisation will be explored, i.e. sex (M/ F), obesity class ($<40/\geq40$ kg/m 2), and SU level ($< 6/\geq6$ mg/dL). We aim to assess whether data provide evidence of superiority of ID to CD group (primary objective). Thus, the primary null hypothesis is no difference between treatments at endpoint (week 16). Response variables (binary outcomes; e.g. the proportion of patients losing more than 5% of baseline weight) will be analysed with a logistic regression model, including the same fixed effects (covariates) as for the analyses of continuous outcomes.

Data monitoring

Careful conduct of the clinical trial according to this protocol has a major impact on the credibility of the results. Careful monitoring will ensure that difficulties are noticed early and their occurrence or recurrence minimised. There are two distinct types of monitoring that generally characterise RCTs: (1) The oversight of the quality of the trial, while the other type involves (2) Breaking the blinding to make treatment comparisons (that is, interim analysis). Both types of trial monitoring, in addition to entailing different staff responsibilities, involve access to different types of trial data and information, and thus different principles apply for the control of potential statistical and operational bias.

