For the purpose of overseeing the quality of the trial, the checks include whether the protocol is being followed, the acceptability of data being accrued, the success of planned accrual targets, the appropriateness of the design assumptions, success in keeping patients in the trials, etc. To maintain the overall quality and legitimacy of the short term RCT, code breaks will occur only in exceptional circumstances when the PI's knowledge of the actual treatment (i.e., ID group) is absolutely essential for further management of the participant. The PI will monitor each participant for clinical and laboratory evidence of adverse events (AEs) on a routine basis throughout the trial. AEs, whether in response to a query, observed by site personnel, or reported spontaneously by the participant, will be recorded. The investigator will assess and record any AE in detail, including the date of onset, description, severity, duration and outcome, relationship of the AE to trial diet, and any action(s) taken. The PI will maintain the blind as far as possible. The actual allocation must NOT be disclosed to study personnel including other site personnel, monitors, corporate sponsors or project office staff; nor should there be any written or verbal disclosure of the code in any of the corresponding participant documents (i.e. except for the materials being provided directly from the dietitian).

We will NOT perform any "interim analyses". Interim analysis would involve the accruing of comparative treatment results. Interim analysis requires unblinding (that is, key breaking) access to treatment group assignment (actual treatment assignment or identification of group assignment) and comparative treatment group summary information. This would necessitate that the protocol (or appropriate amendments prior to the 1st analysis) contains statistical plans for the interim analysis to prevent certain types of bias.

Concomitant Medical Therapy

There are no restrictions to concomitant medical or physical therapy. The participants can at all times request a consultation with the investigator(s) or his/her delegates if the course of the gout is unsatisfactory. These consultations may result in treatment (as judged by the investigator), and will be recorded in the CRF. This does not exclude the participant from the trial.

Harms (collecting, assessing, and reporting of adverse events)

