#### Baseline patient characteristics

Patients will be described with respect to all variables shown in Table 1 in 'Proposed outline of tables and figures' below, separately for the two randomized groups. Data from the baseline visit will be used.

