## Proposed outline of tables and figures:

**Figure 1: CONSORT flow diagram**

[figure not shown]
**Table 1:** Baseline characteristics

| Baseline characteristics               |              |              |                  |
|--|--------------|--------------|------------------|
| Variables                              | ID
(n=XX) | CD
(n=XX) | Total
(n=XXX) |
| Age, years                             |              |              |                  |
| Male sex, n(%)                         |              |              |                  |
| Ethnicity (Caucasian), n(%)            | 100%         | 100%         | 100%             |
| Body weight, kg                        |              |              |                  |
| BMI, m/kg                  |              |              |                  |
| BMI $\geq 40$ kg/m  , n(%) |              |              |                  |
| Duration of gout, years                |              |              |                  |
| Serum urate, mg/dL                     |              |              |                  |
| Serum urate $\geq 6$ mg/L, n(%)        |              |              |                  |
| Presence of palpable tophi, n(%)       |              |              |                  |
| Comorbidity:                           |              |              |                  |
| Kidney stones, n(%)                    |              |              |                  |
| Gall stones, n(%)                      |              |              |                  |
| Cardiovascular disease, n(%)           |              |              |                  |
| Diabetes, n(%)                         |              |              |                  |
| Hypertension, n(%)                     |              |              |                  |
| Hyperlipidemia, n(%)                   |              |              |                  |
| Any urate lowering therapy, n(%)       |              |              |                  |
| Any anti-inflammatory medication:      |              |              |                  |
| Colchicine, n(%)                       |              |              |                  |
| NSAID, n(%)                            |              |              |                  |
| Prednisone, n(%)                       |              |              |                  |
| Outcome Measures:                      |              |              |                  |

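### Must the SAP report urate-lowering therapy after baseline before the week-16 serum urate comparison can be relied on?

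*Protocol*

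**What the plan says.** The protocol (Concomitant Medical Therapy) places no limit on other treatment: "There are no restrictions to concomitant medical or physical therapy". Participants whose gout is unsatisfactory may ask for a consultation, and "These consultations may result in treatment (as judged by the investigator), and will be recorded in the CRF".

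The trial is open. The Blinding section says "blinding of staff or participants will not be feasible" and, in general terms, that "Lack of blinding may also influence compliance with the intervention, use of co-interventions, and risk of dropping out of the trial". Data monitoring adds a partial safeguard: "The PI will maintain the blind as far as possible".

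Protocol Table 2 lists allopurinol, febuxostat, probenecid and benzbromarone as yes/no items (for example "Allopurinol, y/n"), each marked at enrolment and at the 16-week endpoint. There is no week-8 record and no dose.

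The SAP schedule (Section 3, Timing of outcome assessments) carries the same four rows with a mark at baseline only. The single SAP output on these drugs is the row "Any urate lowering therapy, n" (%) in the proposed Table 1, for which "Data from the baseline visit will be used".

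The SU model (SAP Section 6, Analysis methods) contains diet group, time, their interaction and baseline SU. The sensitivity analyses concern missing data, and a further appendix table adjusts for the stratification factors. None involves urate-lowering therapy.

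**The concern.** Urate-lowering drugs act directly on SU, and SU stands second in the test hierarchy, just after body weight. Both staff and participants know the arm, drugs may be started or stopped freely, and the protocol itself names co-interventions as something that lack of blinding can influence. If such changes differed between arms, part of the SU difference could come from drugs rather than diet, or a real diet effect could be masked.

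The SAP's Aims and Hypotheses say that weight loss will bring urate down. A reader who wants to test that claim against the obvious rival explanation would look for drug use by arm at week 16. The protocol schedules that item and the SAP does not show it. So the SAP seems to have dropped something needed to interpret a key secondary outcome.

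**Working it through.** **1. The two schedules.** The discrepancy is real. Enrolment and week 16 are marked in the protocol, baseline alone in the SAP. But the SAP schedule is a reduced list throughout. Compared with Protocol Table 2 it also leaves out lipids, HbA1c, glucose, waist, hip, blood pressure, pulse, metabolic syndrome and all imaging, and it cuts the anti-inflammatory and concurrent-medication rows to baseline in the same way. It reads as the scope of the main report. Data collection is set by the protocol, and the SAP table list is headed as a proposed outline.

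**2. What the SU test estimates.** SAP Section 4 (Analysis populations) keeps patients in their assigned group whatever they do afterwards. With concomitant therapy unrestricted, a drug change is not even a deviation. The contrast is therefore SU under assignment to the intensive diet versus assignment to the conventional diet, later drug changes included. Randomisation protects that contrast. In the SU objective, intensive weight loss serves as the name of the arm: the SAP's multiplicity paragraph and the footnote to Protocol Table 2 use it the same way, and the body-weight objective uses the same phrase, where a causal reading would be circular. Only the Aims and Hypotheses carry the mediation idea, and no planned test evaluates it.

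**3. The plan's own SU figure.** Inputs from the sample-size sections: 30 per arm, SD 1.6 mg/dL, difference 1.2 mg/dL, two-sided 5%.

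- Standard error = 1.6 × √(2/30) = 0.413 mg/dL
- Noncentrality = 1.2 / 0.413 = 2.90, with 58 degrees of freedom
- Power = 0.815, which reproduces the stated 81.5%
- Smallest significant difference = 2.002 × 0.413 = 0.83 mg/dL

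**4. Scale of a possible imbalance.** The documents give no per-patient effect of a drug change and no expected number of changes. The 1.2 mg/dL is a power input, not a bound on a drug effect. Assumed effects of 0.6, 1.2 and 3.0 mg/dL are used only to show the range.

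Shift in the SU difference = (net extra patients with a change in one arm / 30) × assumed effect.

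| Assumed effect (mg/dL) | Net 1 of 30 | Net 3 of 30 | Net 6 of 30 |
|---|---|---|---|
| 0.6 | 0.02 | 0.06 | 0.12 |
| 1.2 | 0.04 | 0.12 | 0.24 |
| 3.0 | 0.10 | 0.30 | 0.60 |

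As a share of 1.2 mg/dL, 3 patients give 5% to 25% and 6 patients give 10% to 50%. Equal changes in both arms give no shift. In the most adverse corner, with 6 net changes in the conventional arm at 3.0 mg/dL each, a difference of 1.2 would become 0.60 and power would fall to 0.298. These are not errors of the planned test: if drug use follows from assignment, the shifted value is the effect of assignment. A descriptive table would change neither the estimate nor the power.

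**5. Whether an analysis would do better.** Adjusting for a drug change means conditioning on something that happens after randomisation, which can itself bias the comparison. Setting SU to missing after a change needs the date of the change, and status at two visits does not supply it. It also needs the missing-at-random assumption, which is doubtful when unsatisfactory gout prompts the change. And it costs precision. The 95% half-width is t × 1.6 × √(2/n):

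- n = 24 per arm (the plan's 20% dropout case): 0.93 mg/dL
- n = 21: 1.00
- n = 18: 1.08
- n = 15: 1.20, equal to the target difference

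**The case for a change.** The strongest reply is that intention to treat settles validity but not attribution. The SAP invites a causal reading of SU, the open design makes drug imbalance plausible, and the protocol's promised discussion of limitations covers patient-reported outcomes only. Naming a by-arm row in advance costs almost nothing and would prevent a choice made after the SU result is known.

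Part of this stands. A row showing urate-lowering therapy by arm at baseline and week 16 would help readers, and the plan does not commit to one. But nothing in the SAP forbids it, the protocol schedules the item, and treatment given at consultations goes into the CRF. An author describing SU in a gout trial can be expected to supply it.

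The row would also settle less than the objection implies. Yes/no items cannot show dose changes, there is no week-8 record, and changes made outside trial consultations may not appear in detail. Even perfect balance would not prove mediation, because diet content differs and so does dietitian contact: weekly in the first phase for the intensive arm, against three sessions and about 4 hours in all for the conventional arm.

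One uncertainty remains. The SAP describes conduct in the past tense, so its baseline-only marks could reflect what was actually collected. The documents do not say. If so, a change to the SAP would not recover the data.

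**Conclusion.** The schedules differ as described, but no change to the plan is needed. The SU comparison is sound as the effect of diet assignment, the weight endpoint is untouched, and neither the model nor the test order would gain from alteration. What is left is a reporting gap around an untested statement about mechanism, which analysts can fill with a descriptive row from data the protocol already schedules.

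The size of any drug imbalance cannot be derived from the documents. The illustrated 0.06 to 0.60 mg/dL for 3 to 6 net patients of 30 rests entirely on assumed drug effects of 0.6 to 3.0 mg/dL, and its direction is unknown. The conclusion relies on two readings: that the SU result is taken as an effect of assignment, as the SAP's analysis population implies, and that the protocol schedule, not the shortened SAP list, governed data collection.
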